6.2 Determination of Sample Size

There are 2 primary endpoints for this study: CRc rate and OS. To maintain strong control of the type I error rate at 0.05, a fallback procedure proposed by Wiens will be used in the testing of the primary endpoints, with an alpha of 0.01 pre-assigned to CRc rate and an alpha of 0.04 pre-assigned to OS (Wiens 2005).

The sample size was calculated based on maintaining 90% power to test both primary endpoints and to account for 2 planned interim analyses for OS, one futility analysis at 30% and one interim efficacy analysis at 60% of the targeted number of OS events, using the O'Brien-Fleming method.

For the primary endpoint of CRc rate, at least 308 patients are required to provide 90% power to detect an improvement in CRc rate from 20% to 40% using a chi-square test at a significance level of 0.01.

For the primary endpoint of OS, approximately 354 OS events are required to provide 90% power to detect a hazard ratio of 0.70 (12.9 months median OS in the experimental arm [vadastuximab talirine plus HMA] versus 9 months for the comparator arm [placebo plus HMA]) using a log-rank test at a 2-sided alpha of 0.04.

To provide adequate power for both primary endpoints, a total of 540 patients will be randomized in a 1:1 ratio to either the experimental arm or the comparator arm, assuming an accrual period of 26 months with a slower rate of accrual for the first 6 months, a 12-month follow-up from the last patient enrolled to the final analysis of OS (after approximately 354 OS events have occurred), and a 5% yearly drop-out rate.

EAST (Version 6.3) was used to calculate and validate the sample size.

6.3 Randomization and Blinding

This is a randomized, double-blind, placebo-controlled, comparative study that will enroll approximately 540 patients in a 1:1 manner.

Randomization will be stratified by:

- Cytogenetic risk per revised UK Medical Research Council (MRC) classification (intermediate versus adverse)
- ECOG performance status (0–1 versus 2)
- HMA (azacitidine versus decitabine)
- Age (<75 years versus \geq 75 years)

Fixed block randomization will be performed centrally using a system that will assign a unique patient randomization number. The actual treatment assignment will remain blinded. Randomization procedures are detailed in the Study Manual.

6.4 Data Transformations and Derivations

Age as entered in the CRF will be used for any calculations and analyses, if available. If age is not available, age in years will be calculated with the SAS INTCK function using consent date and birth date.

Study Day will be calculated as (Date of Visit [or Event] – Date of Randomization + 1) for dates on or after randomization. For dates prior to randomization, Study Day will be calculated as (Date of Visit [or Event] – Date of Randomization).

Other time variables based on two dates (e.g., Start Date and End Date) will be calculated as (End Date – Start Date + 1) (in days) unless otherwise specified in the planned analysis section.

The following unit conversion will be implemented unless otherwise specified:

Months = Days / 30.4375

Years = Days / 365.25

Baseline values used in all analyses will be the most recent non-missing measurement prior to the first dose of study treatment (HMA or blinded study drug). For patients who did not receive any study treatment, baseline is the last non-missing measurement on study.

At baseline, if both bone marrow biopsy and aspirate results are available, the biopsy result will be used as the baseline bone marrow blasts. The only exception will be if the biopsy result is blasts <20% and the patient was qualified for the study based on the aspirate result (blasts \geq 20%), then the aspirate result will be used as the baseline bone marrow blasts.

The EOT date will be the date the EOT visit is performed, or 30 days after the last dose of any study treatment if an EOT visit is not performed.

For efficacy analysis, if the response is determined to be progression or disease relapse, the earliest date of the bone marrow examination or CBC (within a 14 day window from the bone marrow examination) that supports the overall response assessment at a given visit will be the response assessment date. For any other responses (CR, CRi, mLFS, partial response, anti-leukemic effect, and stable disease), the latest date of the bone marrow examination or CBC (within a 14 day window from the bone marrow examination) that supports the overall response assessment at a given visit will be the response assessment date.

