### **6.2.1 Baseline Visit (Days –7 to Day 1)**

- Physical exam

- Height and weight
- Electrocardiogram (ECG)
- Pulse oximetry testing for oxygen saturation level at room air
- Pregnancy test for females of childbearing potential
- ECOG performance status ([Appendix C](#))
- Collection of data to calculate the Charlson Comorbidity Index (CCI), the Hematopoietic Cell Transplantation-Specific Comorbidity Index (HCT-CI), and Wheatley Risk group
- Serum chemistry panel
- Complete blood count (CBC) with differential
- EQ-5D
- EORTC-QLQ-C30
- Randomization (to occur within 1 business day of planned first dose of HMA).

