5 ANALYSIS SETS

5.1 Intent-to-Treat Analysis Set

The intent-to-treat (ITT) analysis set will include all randomized patients. Patients will be included in the treatment group assigned at randomization regardless of the actual treatment received.

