5.3 Safety Analysis Set

The safety analysis set will include all patients who receive any dose of blinded study treatment (vadastuximab talirine or placebo) or HMA. Treatment group will be determined using the actual treatment received, regardless of the randomization treatment assignment. Patients receiving any dose of vadastuximab talirine will be grouped into the experimental arm. Patients who do not receive vadastuximab talirine but receive any dose of HMA will be grouped into the comparator arm.

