6.8 Examination of Subgroups

As exploratory analyses, subgroup analyses may be conducted for selected endpoints (see Section 7). Subgroups may include but are not limited to the following:

- ECOG performance status (0–1, 2)
- Cytogenetic risk by MRC (adverse, intermediate/unknown)
- HMA
- Age (<75, ≥75 years old)

- Age (<80, ≥80 years old)
- Gender
- Race
- Geographic region (North America/Australia, Western Europe/Israel, Eastern Europe, Asia)
- Type of AML (de novo AML, secondary AML)
- AML subtype (AML with recurrent genetic abnormalities, AML with myelodysplasia-related changes, AML with therapy-related myeloid neoplasms, AML not otherwise specified)
- Underlying myelodysplasia (yes, no)
- Prior hematological disorder (yes, no)
- Mutational abnormalities (NPM1+, NPM1-)
- Medically unfit for intensive therapy (yes, no)
- Baseline bone marrow blast percentage (20% - 30%, >30%)
- Baseline bone marrow blast percentage (20% - 50%, >50%)
- Baseline WBC (≤5,000, >5,000/μL)
- Baseline WBC (<10,000, ≥10,000/μL)
- Baseline WBC (<15,000, ≥15,000/μL)
- Remission status (CRc, non-responders)
- MRD-negative remission status (MRD-negative CRc, MRD-positive CRc, non-responders)
- Charlson Comorbidity Index (low, moderate, high)
- Hematopoietic Cell Transplantation-Comorbidity Index (HCT-CI; low, intermediate, high)
- Wheatley Risk group (good, standard, poor)
- European ALMA score (favorable, intermediate, unfavorable)
- Treatment-related mortality (TRM) score (low, intermediate, high)

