7.2 Demographic and Baseline Characteristics

Demographics and baseline characteristics, including age, gender, ethnicity, race, height, weight, and ECOG score will be listed and summarized; summaries will be presented by treatment group and total using the ITT analysis set.

Disease specific characteristics, including time from initial AML diagnosis, baseline bone marrow blast percentage, baseline WBC, AML subtype, prior hematologic disorder, cytogenetic risk group, mutational abnormalities, Wheatley risk group, European ALMA score, TRM score, Charlson comorbidity index and HCT-CI, will be summarized by treatment group and total using the ITT analysis set. In addition, the number and percentage of patients who receive at least one prior anticancer therapy for hematological disorder will be summarized.

Reasons for enrollment and reasons patients are medically unfit to receive intensive therapy will be summarized by treatment group and total using the ITT analysis set.

The stratification factors entered at the time of randomization and the actual strata at baseline for each patient will be presented in a listing.

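### The SAP baseline rule for randomised but never-treated patients has no upper time limit, so a later value can be labelled baseline

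*SAP*

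**What the plan says.** SAP 6.4 gives two baseline rules. The general one is: "Baseline values used in all analyses will be the most recent non-missing measurement prior to the first dose of study treatment". The exception follows: "For patients who did not receive any study treatment, baseline is the last non-missing measurement on study". The first rule ends at a fixed event, the first dose. The second ends only when the patient's data end.

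Never-treated patients are in the ITT set (SAP 5.1): "The intent-to-treat (ITT) analysis set will include all randomized patients". SAP 7.2 uses that set for the demographic and baseline tables, which include weight and ECOG: "summaries will be presented by treatment group and total using the ITT analysis set". It also uses it for the disease tables: "Disease specific characteristics, including time from initial AML diagnosis, baseline bone marrow blast percentage, baseline WBC, AML subtype". SAP 6.8 lists subgroups by baseline marrow blasts and by three WBC cut-points, and SAP 7.5.1.2 says OS may be examined in them.

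The safety set excludes these patients (SAP 5.3): "The safety analysis set will include all patients who receive any dose of blinded study treatment (vadastuximab talirine or placebo) or HMA".

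**The concern.** A baseline value should describe the patient at entry. Under the exception, the latest value on record becomes baseline whenever it was taken. For a patient who was randomised, held back from dosing and never started, that value may reflect what happened after entry.

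Two outputs are exposed. The ITT baseline tables could show a state that arose after randomisation. A WBC might even exceed the entry limit of 30,000/µL (Protocol 4.1) and make an eligible patient look ineligible. In an OS subgroup by baseline WBC, a patient could be placed by a value that post-dates randomisation, so that membership is no longer fixed at entry.

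**Working it through.** The plan gives no figure on this point to reproduce. The check sets the provisions side by side and then bounds the number of patients.

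**1. Is there a cap elsewhere?** Neither document limits the exception in SAP 6.4. Protocol 9.3.1.6, on derivations, deals only with response and relapse dates.

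**2. Can a later value exist?** The protocol ties randomisation to the intended start: "Randomization (to occur within 1 business day of planned first dose of HMA" (Protocol 6.2.1). If dosing is then held for abnormal laboratory results, the blood count and chemistry panel still go to the central laboratory (Protocol 6.3.1). A patient held in this way and never dosed can therefore have a WBC dated after the planned start. This is the one route the documents describe.

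**3. How common is it likely to be?** Most of the schedule presupposes dosing:
- Day 1 is the first HMA dose (Protocol 6.1), and cycle visits count from it.
- The end-of-treatment visit is timed from the last dose (Protocol 6.4).
- Survival contact starts after end of treatment, and follow-up blood counts are for patients who stop treatment (Protocol 6.5).
- Response marrows are scheduled late in even-numbered cycles, around response or relapse, and at end of treatment or follow-up (Protocol 6.3.8, 6.4 and 6.5).

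For many never-treated patients, the last value on study will still be the screening or baseline-visit value.

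**4. What does the rule reach?**
- ITT baseline tables (SAP 7.2): yes.
- OS subgroups by baseline WBC (SAP 6.8, 7.5.1.2): yes, if they are run.
- CRc: no. CR and CRi rest on absolute marrow and blood-count criteria (Protocol Appendix E), not on change from baseline.
- Overall OS: no. It runs from randomisation to death (SAP 7.5.1.2).
- Stratification factors used for adjustment: no. They come from the randomisation record (SAP 6.9).
- Laboratory change from baseline and ECOG shift tables: no. They use the safety set (SAP 7.6).

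**5. How many patients?** The final analysis has 240 randomised patients (SAP 6.10). The untreated share is not given, so it is assumed:
- 1%: 240 × 0.01 = 2.4, about 2
- 3%: 240 × 0.03 = 7.2, about 7
- 5%, as a wider case: 240 × 0.05 = 12

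These are the patients under the rule. Only those with a later value change. One patient crossing a WBC cut-point moves the pooled percentage by 1/240, or 0.4 percentage points.

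**The case against.** The strongest reply is that the exception has almost nothing to act on. With visits timed from dosing, a never-dosed patient has essentially no scheduled later assessment. All efficacy output is descriptive (SAP 6.7 and 7.5), and the WBC subgroups are optional and exploratory. This stands, and it sets the size of the point. It does not make the wording right, because the held-dose blood count is a documented route.

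A second reply is that post-randomisation timing is not peculiar to untreated patients. Someone whose first dose is delayed and then given also takes the delayed value as baseline. That is correct. The defect is therefore the missing upper bound, not post-randomisation timing as such: a treated patient's baseline always stops at first dose.

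A reader might infer more than the documents support:
- **Values near death or withdrawal.** Nothing in the schedule provides for a terminal measurement in a never-dosed patient, so systematic sorting of early deaths into poor-prognosis subgroups is conjecture.
- **Marrow blasts.** Every scheduled marrow after screening presupposes treatment. In practice the baseline marrow is the diagnostic sample.
- **ECOG subgroups.** ECOG is a stratification factor, and SAP 6.9 takes those factors from randomisation for stratified analyses. SAP 7.2 lists both randomised and actual strata, and the SAP does not say which defines the ECOG subgroup. Contamination there is uncertain.
- **Visible shifts in subgroup estimates.** The documents give no subgroup sizes, so no such effect can be calculated.

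**Conclusion.** The point holds as a minor wording defect. SAP 6.4 leaves baseline for never-treated ITT patients without an upper time limit, so a later value, most plausibly a WBC, can displace the true one. The exposure is the ITT baseline tables and the exploratory OS subgroups by baseline WBC.

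At an assumed 1–3% untreated, 2–7 of 240 patients fall under the rule, and probably fewer change. The assumed share is the only numerical assumption. That few patients have a later value is inferred from the visit schedule; the documents do not report it. No primary result, design figure or safety table depends on this point.

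**What to change.** Replace the exception in SAP 6.4 with a capped rule, for example: *if a randomised patient was never dosed, baseline is the latest non-missing value dated no later than the date of randomisation or the planned date of the first HMA dose (Cycle 1 Day 1), whichever is later.*

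The planned Day 1 is needed in the cap. The baseline visit window runs to Day 1 (Protocol 6.2.1) and randomisation may come up to one business day before the first HMA dose (Protocol 5.2.2). A strict cut at randomisation could therefore discard a valid baseline-visit value in untreated patients while the same value is kept in treated ones.

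The cost is one sentence, plus having the planned first-dose date available for these few patients; the documents do not say whether it is recorded. A value taken after the cap is no longer used as baseline, which is the intent. No sample size, endpoint or test changes. SAP Section 1 gives the route: amend before database lock, or document the change in the CSR. If no never-treated patient has a value after the cap, no result changes.

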6.5 Handling of Dropouts and Missing Data

Missing data will not be imputed unless otherwise specified. Missing AE dates will be imputed while calculating duration of events and treatment emergent status. Missing subsequent anticancer therapy start date will be imputed while deriving time-to-event endpoints as applicable (see Appendix A and B for imputation details). Missing data in PRO assessment will be handled according to the questionnaire's standard guidelines. Patients with a missing value for a variable other than response or time-to-event endpoints (e.g., CRc

rate and OS) will be excluded from the analysis of that endpoint. Censoring rules will be applied in the analysis of time-to-event endpoints as detailed in Section 7.5.

6.6 Multicenter Studies

There are multiple centers in this study, however it is not anticipated that any center will accrue enough patients to warrant an analysis by center.

6.7 Multiple Comparison/Multiplicity

To maintain strong control of the Type I error rate at 0.05, the fallback procedure proposed by Wiens will be used in the testing of primary endpoints, with an alpha of 0.01 pre-assigned to CRc rate and an alpha of 0.04 pre-assigned to OS (Wiens 2005). If the test for the CRc rate is statistically significant, then the alpha of 0.01 will be re-allocated to OS, and the test for OS will be performed at a 2-sided alpha of 0.05. If the test for the CRc rate is not statistically significant, then the test for OS will be performed at a 2-sided alpha of 0.04.

The parallel gatekeeping principle will be used to control the overall type I error rate of 0.05 (Dmitrienko 2011). The primary endpoints, CRc rate and OS (family 1), will be the gatekeepers for testing the secondary endpoint of MRD-negative CRc rate (family 2). If at least one of the primary endpoints is statistically significant, then a statistical test will be performed for the MRD-negative CRc rate. If both CRc rate and OS are statistically significant, then MRD-negative CRc rate will be tested at an overall alpha of 0.05. If only one of the 2 primary endpoints is statistically significant, then MRD-negative CRc rate will be tested at the corresponding alpha level of the significant primary endpoint. If the tests for both CRc rate and OS are not statistically significant, then the p-value of the test for MRD-negative CRc rate will still be calculated but considered descriptive.

Two formal interim analyses for OS are planned. The test significance level for OS at the interim analysis will be adjusted based on the actual number of OS events observed at each interim analysis according to the O'Brien-Fleming spending function.

Due to safety concerns raised by the IDMC, the study was terminated early prior to the first interim analysis planned in the protocol. Final analysis will be performed based on 240 patients randomized into the study by the time enrollment was closed. All efficacy analysis will be descriptive in nature and no multiple testing procedure will be applied.

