#### **9.3.5.1 Primary Efficacy Analysis**

**CRc rate** will be analyzed based on the ITT analysis set. The CRc rate between the 2 treatment arms will be compared using a Cochran-Mantel-Haenszel test stratified by the randomization strata. The CRc rate and its 2-sided 99% confidence interval (CI) will be summarized by treatment arm. At the time of the primary analysis of CRc rate, only the first 308 patients randomized will be included in the population for the analysis of CRc rate. CRc rate will also be analyzed for all randomized patients at the time of the final analysis.

**Overall survival** will be assessed using Kaplan-Meier methods. A stratified log-rank test without adjustments for covariates will be used in the primary evaluation of OS differences between the 2 treatment arms based on the ITT population. The hazard ratio will be estimated using the unadjusted stratified Cox model. The 2-sided 95% CI and the CI corresponds to the significance level of the test following the multiplicity adjustment (see Section [9.3.1.5](#)) will be presented. The proportional hazard assumptions will be examined and sensitivity analyses

will be conducted if appropriate. All events entered in the database at the time of the analysis and source-data verified will be included in the analysis of OS, even if there is more than the pre-specified number of events.

Kaplan-Meier curves depicting OS in the 2 treatment arms will be generated. Additionally, the median OS and the probability of OS from 1 month to the end of the follow-up period will be reported at pre-specified intervals. The associated 2-sided 95% CIs will be calculated using the complementary log-log transformation method (Collett 1994). Detailed methodology will be provided in the SAP.

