1 INTRODUCTION

This document outlines the statistical methods to be implemented within the scope of Protocol SGN33A-005, entitled “A randomized, double-blind phase 3 study of vadastuximab talirine (SGN-CD33A) versus placebo in combination with azacitidine or decitabine in the treatment of older patients with newly diagnosed acute myeloid leukemia (AML)”. Results of the proposed analyses will become the basis of the clinical study report (CSR) for this protocol.

The purpose of this plan is to provide specific guidelines from which the analysis will proceed. All planned analyses specified in this document will be performed. Any changes to this plan, in the form of “post hoc” or “data driven” analyses will be identified as such in the final CSR. Any changes will either be reflected in amendments to this plan before the database lock or specifically documented in the CSR.

Due to safety concerns raised by the IDMC, the study was terminated early prior to the formal interim analyses planned in the protocol. Final analysis will be performed based on 240 patients randomized into the study by the time enrollment was closed. This SAP reflects the proposed analyses for the abbreviated CSR.

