6 STATISTICAL CONSIDERATIONS

6.1 General Principles

Descriptive statistics (mean, median, standard deviation, minimum and maximum) will be used to summarize continuous variables. Frequencies and percentages will be used to summarize categorical variables. The median survival time will be estimated using the Kaplan-Meier method; the associated confidence interval (CI) will be calculated based on the complementary log-log transformation (Collett 1994).

Unless otherwise specified, all statistical tests will be performed using a two-sided alpha of 0.05. Confidence intervals will be calculated at a two-sided 95% level. Multiplicity adjustment for alpha level is discussed in Section 6.7.

Any analysis not described in this plan will be considered exploratory, and will be documented in the CSR as a post hoc analysis or a change to the planned analysis.

To comply with regulatory electronic submission guidelines, listings of all clinical data will be submitted as electronic data sets. To facilitate data review for the study report, only pertinent data listings will be created and attached to the appendix of the CSR.

All statistical tables, listings, and figures will be produced using SAS[®], version 9.3 or more recent. Other statistical software, if used, will be described in the CSR.

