7.5.1 Primary Endpoint

7.5.1.1 Composite Complete Remission (CRc) Rate

CRc rate is defined as the proportion of patients achieving CR or CRi prior to the start of subsequent anticancer therapy or stem cell transplant. Patients whose disease response cannot be assessed will be considered non-responders in the calculation of CRc rate. The CRc rate and the 2-sided 95% CI will be summarized by treatment group.

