9 CHANGES FROM PLANNED ANALYSES

9.1 Changes from the Protocol

Not Applicable.

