9.2.3 Version 4 Changes

The study was terminated early due to safety concerns raised by the IDMC. The SAP was updated to include only analyses required for the abbreviated CSR. Changes from version 3 are summarized below:

- Sec 6.7: Clarify that all efficacy analyses will be descriptive in nature and no multiple testing procedure will be applied
- Sec 6.10: Clarify that no interim analysis will be conducted and final analysis will be based on 240 patients randomized into the study by the time enrollment was closed
- Sec 7.1: Remove the summary of screen failed patients
- Sec 7.5: Remove all efficacy analyses other than the descriptive summary of CRc rate, OS, MRD-neg CRc rate, and early mortality rate
- Sec 7.6.1: Add additional summary of AEs of special interest
- Sec 7.6.2: Add additional summary to evaluate the extent of neutropenia
- Sec 7.7: Remove the analyses of PRO endpoints, transfusion, MRU, and subsequent therapy
- Sec 8: Clarify that no interim analysis will be conducted and final analysis will be based on 240 patients randomized into the study by the time enrollment was closed

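### Does the empty change record in SAP 9.1 matter, given that SAP 6.7 drops the protocol's testing procedure and SAP 7.5.1.1 its 99% interval for CRc?

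*SAP*

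**What the plan says.** Protocol 9.3.1.5 sets a fallback procedure. CRc is tested at 0.01 and OS at 0.04, and OS rises to 0.05 if CRc is significant. Remission with negative minimal residual disease (MRD-negative CRc) follows: at 0.05 if both primaries succeed, otherwise at the level of the one that did. Protocol 9.3.5.1 plans a stratified Cochran-Mantel-Haenszel (CMH) test of CRc and adds: "The CRc rate and its 2-sided 99% confidence interval (CI) will be summarized by treatment arm". For OS: "A stratified log-rank test without adjustments for covariates will be used in the primary evaluation of OS differences", with a stratified Cox hazard ratio.

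SAP 6.7 repeats the whole multiplicity rule. Its last paragraph then reports early termination with 240 patients and says: "All efficacy analysis will be descriptive in nature and no multiple testing procedure will be applied". SAP 7.5 contains no tests. For CRc: "The CRc rate and the 2-sided 95% CI will be summarized by treatment group". This agrees with the general rule in SAP 6.1: "Confidence intervals will be calculated at a two-sided 95% level".

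On the record of changes, SAP 9.1 (changes from the protocol) reads "Not Applicable". SAP 9.2.3, which lists changes from SAP version 3, says: "Clarify that all efficacy analyses will be descriptive in nature and no multiple testing procedure will be applied". SAP 1 sets the policy: "Any changes will either be reflected in amendments to this plan before the database lock or specifically documented in the CSR".

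**The concern.** A reader who opens SAP 9.1 is told that nothing departs from the protocol. In fact every planned test of both primary endpoints has gone, and the interval for one of them has moved from 99% to 95%. The 99% level pairs with the alpha of 0.01 given to CRc, so it looks deliberate, and its replacement is explained nowhere. The abbreviated clinical study report (CSR) is to be built on this SAP and could carry the error forward.

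A second worry sits in the retained text of SAP 6.7, which still says in the future tense that gatekeeping holds overall type I error at 0.05. Under the rule as written, the 0.01 earned by CRc passes in full to OS and is then used again for MRD-negative CRc. If someone relied on the statement, a claim on the secondary endpoint would rest on error control that does not quite exist.

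**Working it through.** **1. The design figures reproduce at the stated alphas.** Inputs from Protocol 9.1 and SAP 6.2.

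- CRc: 20% against 40%, two-sided 0.01, 90% power. Per arm, n = [2.576·√(2·0.3·0.7) + 1.282·√(0.16 + 0.24)]² / 0.2² = 153.7, so 154 per arm and 308 in total, as stated.
- OS: hazard ratio 0.70, two-sided 0.04, 90% power. Events = 4·(2.054 + 1.282)² / (ln 0.70)² ≈ 350. With one efficacy look at 212 of 354 events under O'Brien-Fleming-type spending, 352.1 events give 90% power and 354 give 90.2%. This agrees with the stated 354.

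**2. What changed, and where the SAP shows it.**

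| Item | Protocol | SAP | Shown in the SAP |
|---|---|---|---|
| Fallback and gatekeeping | 9.3.1.5 | not applied | 6.7 and 9.2.3, with reason |
| OS interim looks | 9.3.10 | none | 6.10, 8 and 9.2.3, with reason |
| CMH, log-rank, Cox | 9.3.5.1, 9.3.5.2 | absent from 7.5 | 9.2.3 keeps descriptive summaries only |
| CRc interval | 99% | 95% | text of 6.1 and 7.5.1.1; in no change list |
| CRc and MRD-negative CRc definitions | 9.2.1.1, 9.2.2.1 | only remissions before later therapy or transplant | text of 7.5.1.1 and 7.5.2.1; in no change list |
| Supplemental mITT analyses | 9.3.5 | ITT only | text of 7.5; not named in a change list |
| Remission duration, EFS, LFS, time to remission | 9.3.5.2 | not analysed | 7.5.2.2 to 7.5.2.5, with reason |
| Patient-reported outcomes, resource use | 9.3.7, 9.3.8 | removed | 9.2.3 |

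The patient set for CRc is not a change. All 240 patients fall within the first 308 randomized, and Protocol 9.3.5.1 also plans CRc in all randomized patients at the final analysis.

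**3. Size of the interval difference.** Assume 120 per arm (240 at 1:1) and the design rates. Half-width = z·√(p(1−p)/120).

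- p = 0.20: 1.960·0.0365 = 7.2 points at 95%; 2.576·0.0365 = 9.4 at 99%.
- p = 0.40: 1.960·0.0447 = 8.8 points at 95%; 2.576·0.0447 = 11.5 at 99%.
- Exact limits: 24/120 gives 13.3 to 28.3% (95%) and 11.5 to 30.9% (99%); 48/120 gives 31.2 to 49.3% and 28.7 to 52.2%.

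The ratio 1.960/2.576 = 0.76 is fixed by the two levels. Both documents give the interval for each arm's own rate, so neither level decides the comparison between arms. A reader can compute the 99% limits from the reported counts.

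**4. The gatekeeping rule.** Three hypotheses give 2³ − 1 = 7 configurations with at least one true null.

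- CRc and OS both null, whatever holds for MRD-negative CRc (two configurations): 1 − 0.99·0.96 = 0.0496 if independent, at most 0.05. When MRD-negative CRc is null too, a false claim on it first requires a false claim on a primary.
- CRc and MRD-negative CRc null, OS effective: 0.01 + 0.99·0.04 = 0.0496, at most 0.05.
- A single null (three configurations): at most 0.05, the largest level any one test receives.
- OS and MRD-negative CRc null, CRc effective: OS is tested at 0.05 and MRD-negative CRc at 0.01, so 1 − 0.95·0.99 = 0.0595 if CRc always succeeds. At 90% CRc power, 0.9·0.0595 + 0.1·0.04 = 0.0576. The bound under any dependence is 0.05 + 0.01 = 0.06.

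A simulation with MRD-negative CRc as a subset of CRc (2 million trials per case, futility look ignored, assumed MRD-negative rates of 5 to 15% in both arms, OS–MRD correlation 0 to 0.6) gives 0.052 to 0.057. The configuration is also narrow: CRc doubles from 20% to 40% while MRD-negative CRc stays put, so at a 10% MRD-negative rate the share of remissions that are MRD-negative falls from 10/20 = 50% to 10/40 = 25%.

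**The case for a change.** The best case for a change is that SAP 9.1 is wrong on its face and could be put right in a few lines. SAP 9.2 compares SAP versions, so it does not answer the question that 9.1 asks. The interval level and the narrowed remission definitions appear in no list at all, and both concern a primary endpoint. Protocol 9.3 explains why no protocol amendment is needed, but that does not make 9.1 accurate. And a statement of 0.05 control that fails in one configuration should not stand unqualified.

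The factual part of this stands: the entry is inaccurate, and the control statement is sound only for CRc and OS.

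The predicted harm does not follow. SAP version 3 was aligned to protocol amendment 3 (SAP 9.2.2), which is the current protocol, so the version 4 list is in substance a list of departures from the protocol, made by the SAP-amendment route that SAP 1 allows. A CSR author would have to overlook SAP 1, 6.7, 6.10, 7.5, 8 and 9.2.3 to report no change. The 95% level follows from the decision not to test: with no alpha of 0.01 left to match, the default in SAP 6.1 applies. The control statement is withdrawn in the same section that makes it.

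**Conclusion.** The point is correct as a matter of record-keeping, but it calls for no change to the plan. SAP 9.1 is a clerical slip in a document that elsewhere states what was dropped and why. Analysts work from SAP 7.5, which is unambiguous on set, estimate and interval level. Reporting efficacy descriptively is a reasonable response to termination before the first interim analysis, and SAP 1 leaves room for any unlisted departures, including the interval level and the remission definitions, to be documented in the CSR.

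In size, the CRc interval is 24% narrower than at the protocol's level (7.2 against 9.4 points, 8.8 against 11.5), with no decision tied to it. The gatekeeping excess is at most 0.01 above 0.05, in one of seven configurations, and has no effect because no test is carried out. It would matter only if the rule were used again or if overall control including MRD-negative CRc were claimed.

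This rests on three assumptions: about 120 patients per arm; CRc rates near the design values for the interval widths; and a CSR author who reads the SAP beyond section 9.1. SAP version 3 is not available, so the step at which the interval moved from 99% to 95% cannot be dated.
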